# **Treatment-emergent Laboratory Abnormality**

A treatment-emergent laboratory abnormality is defined as an increase of at least one toxicity grade from the baseline assessment at any post baseline visit up to and including 14 days after the last dose date of study drug. If no assessment is available at baseline, the screening assessment will be used to assign the baseline toxicity grade. If the relevant baseline and screening assessments are

missing, then any graded abnormality (i.e., at least Grade 1) is considered to be treatmentemergent.

#### **Concomitant Medications**

Concomitant medications are those medications taken on or after the initiation of study drug.

## **Previous Medications**

Previous medications are those medications taken prior to the initiation of study drug.

#### 4.4. TIMING OF ANALYSES

If final results to analyze secondary virologic or PK endpoints are delayed unexpectedly and significantly, then analysis of the clinical data will proceed based on cleaned and locked clinical CRF data and virologic data to identify the ITTI population, and analysis of the secondary virologic and PK endpoints will be performed based on available preliminary results. A final analysis of secondary virologic and PK endpoints will be conducted once final data are available.

Secondary analyses to evaluate the exposure response of peramivir, and to assess changes in influenza viral susceptibility to neuraminidase inhibitors following treatment, may be conducted at a later date, if the required pharmacokinetic and virology data are not available at the time of the analysis of the clinical data.

#### 5. ANALYSIS POPULATIONS

All subjects enrolled (e.g., signed informed consent) will be included in the summary of subject disposition and all data listings. The populations for analysis of safety and effectiveness endpoints will include the Intent-to-Treat (ITT), Intent-to-Treat Infected (ITTI), safety populations, and an exposure-response population.

# 5.1. INTENT-TO-TREAT POPULATION

The ITT population will include all randomized subjects. The ITT population will be the primary population for analyses of demography and subject accountability.

# 5.2. INTENT-TO-TREAT INFECTED POPULATION

The ITTI population will include all subjects who are enrolled, treated, and have influenza confirmed by RT-PCR. The ITTI population will be used for analyses of effectiveness.

# **5.3. SAFETY POPULATION**

The safety population will include all randomized subjects who receive at least one partial dose/injection of study drug. The safety population will be the primary population for all analyses

of safety data.

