2. SYNOPSIS

Name of Sponsor/Company:

BioCryst Pharmaceuticals, Inc.

Name of Investigational Product:

Peramivir

Title of Study:

A Phase 3, randomized, open label, active-controlled study to evaluate the safety, pharmacokinetics and effectiveness of IV peramivir compared to oral oseltamivir in pediatric subjects with acute uncomplicated influenza.

Study Center(s): Multi-center

Principal Investigator:

[name]., Ph.D.

Chief, Pediatric Infectious Diseases

Louisiana State University Health Sciences Center - Shreveport

Studied Period (years):

Phase of Development:

3

Estimated date first subject enrolled: December 2014

Estimated date last subject completed: September 2020

Objectives:

Primary:

• To evaluate the safety of intravenous (IV) peramivir (study drug) compared to oral oseltamivir in pediatric subjects with acute uncomplicated influenza.

Secondary:

- To describe the pharmacokinetics of IV peramivir in pediatric subjects with influenza.
- To evaluate the effectiveness of IV peramivir compared to oral oseltamivir in pediatric subjects with influenza.
- To evaluate the incidence of influenza complications, specifically otitis media, sinusitis, bronchitis or pneumonia requiring antibiotic use diagnosed after initiation of treatment.

Methodology:

Subjects meeting the inclusion/exclusion criteria may be enrolled into the study. It is expected that most subjects will have the Screening/Baseline visit and the Day 1 treatment visit on the same day.

A subject's duration of participation in this study is expected to be 14 days.

Subjects \geq 7 years old will be randomized to 1 of 2 treatment arms:

Treatment Group 1: A single dose of intravenous peramivir

Treatment Group 2: Oral oseltamivir given twice daily (BID) for 5 days

(Note: at the date of amendment 3, the dose cohorts for subjects > 7 years old were fully enrolled and no further subjects > 7 years will be enrolled).

Subjects < 7 years old will receive a single dose of intravenous peramivir.

(Note: at the date of amendment 3, the dose cohort for subjects 2-7 years old was partially enrolled under the previous randomization scheme that allocated subjects to peramivir or oseltamivir. Following FDA feedback, remaining subjects to be enrolled in the 2 to <7 years old cohort, the 28 day to < 2 years old cohort, and the birth to < 28-day cohort, will all be assigned to receive treatment with IV peramivir.

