9.3. Randomization and Blinding/ Masking

Subjects ≥ 7 to 17 years of age will be randomized to 1 of 2 treatment arms, at a ratio of 4:1:

Treatment Group 1: A single dose of IV peramivir

Treatment Group 2: Oral oseltamivir given BID for 5 days

Following approval of amendment 3, all subjects < 7 years old will receive a single dose of intravenous peramivir.

As this is an open label study, blinding is not applicable.

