13.5. Analysis Populations

The populations defined for analysis will include the intent-to-treat (ITT) population, intent-to-treat infected (ITTI) population, safety population, and an exposure-response population. Additional analysis populations may be defined to evaluate study results. Any additional analysis populations will be defined in the SAP.

- Intent-To-Treat Population: The ITT population will include all subjects who are randomized. The ITT population will be used for analyses of accountability and demographics.
- Intent-To-Treat Infected Population: The ITTI population will include all subjects who are enrolled, treated, and have influenza confirmed by RT-PCR. The ITTI population will be used for analyses of effectiveness.
- Safety Population: The safety population will include all subjects who received at least one dose of study drug. This population will be used for all safety analyses.
- Exposure-Response Population: The exposure-response population will include all subjects in the ITTI population who have a quantifiable plasma concentration of peramivir and at least one post-baseline effectiveness assessment. This population will be used for all exposure-response analyses.

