#### 4.2. RANDOMIZATION AND MASKING

Approximately 140 subjects will be enrolled. Up to 10 subjects from birth to < 28 days will be enrolled to receive a single dose of IV peramivir. Up to 20 subjects from 28 days to < 2 years will either be randomized to 1 of 2 treatment arms at a ratio of 4:1 or will receive a single dose of IV peramivir. Up to 110 subjects from 28-days to < 18 years of age will be randomized to 1 of 2 treatment arms at a ratio of 4:1:

- Treatment Group 1: A single dose of IV peramivir
- Treatment Group 2: Oral oseltamivir given BID for 5 days

This is an open label study and as such, blinding is not applicable.

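### SAP 5.3 limits the Safety population to randomized subjects, so children assigned to peramivir without randomization fall out of the primary safety tables as written

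*SAP*

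**What the plan says.** **Safety population.** SAP 5.3: "The safety population will include all randomized subjects who receive at least one partial dose/injection of study drug". The same section makes this the primary set for safety data, and SAP 10 puts the Safety label on Tables 14.3.1.1 to 14.3.8. Protocol 13.5: "The safety population will include all subjects who received at least one dose of study drug".

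**ITT.** Both documents require randomization. Protocol 13.5: "The ITT population will include all subjects who are randomized". SAP 5.1: "The ITT population will include all randomized subjects".

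**ITTI (effectiveness).** SAP 5.2 does not require it: "The ITTI population will include all subjects who are enrolled, treated, and have influenza confirmed by RT-PCR".

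**Who is not randomized.**
- SAP 4.2, on neonates: "Up to 10 subjects from birth to < 28 days will be enrolled to receive a single dose of IV peramivir".
- SAP 2.1 also assigns children aged 28 days to <2 years directly to peramivir if they enter under protocol version 4.0 or later.
- Protocol 9.3 goes further: "Following approval of amendment 3, all subjects < 7 years old will receive a single dose of intravenous peramivir".
- The protocol synopsis adds that the cohort aged 2 to 7 years "was partially enrolled under the previous randomization scheme that allocated subjects to peramivir or oseltamivir", so some of those children were randomized.

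**Declared changes.** SAP 7 lists one departure from the protocol, a count of antipyretic doses, and expects no others.

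**The concern.** The SAP narrows the protocol's Safety population without declaring it, and the children it cuts out are the youngest. Safety is the primary objective. According to the protocol synopsis the older cohorts are full, so the children still to be enrolled under version 6.0 are under 7 and assigned to peramivir. Each of them would be outside the primary safety set as written, yet could count for effectiveness through ITTI.

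These data are hard to replace. The pediatric surveillance study described in protocol 5.3.3 had 1 patient under 4 weeks of age among 1,199, and protocol 5.4 and 9.1 support the regimen for the youngest infants by simulation.

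The ITT definition carries the same condition. It would take the same children out of the demographics table (14.1.3) and out of the summary of plasma concentrations by time point (Table 14.4.1.1).

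**Working it through.** **Membership of a treated child under each definition**

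| Child | Safety, SAP 5.3 | Safety, protocol 13.5 | ITT, both documents | ITTI, if RT-PCR positive |
|---|---|---|---|---|
| Randomized | in | in | in | in |
| Assigned to peramivir | **out** | in | **out** | in |

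**Inputs for the size.** Cohort caps are from protocol 7.2, the 4:1 ratio from protocol 9.3 and SAP 2.1, and the figure of about 117 on peramivir from protocol 13.4. All counts assume that every cohort fills to its cap and that 4:1 holds exactly. I take the SAP's 110 randomized subjects as aged 2 to <18 years (SAP 2.1). SAP 4.2 gives 28 days as their lower age, which would count the under-2s twice.

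1. *Planned total.* 10 + 20 + 10 + 30 + 40 + 30 = 140, as the protocol states.
2. *About 117 on peramivir.* On the SAP scheme, if every child aged 28 days to <2 years was randomized, 10 + 0.8 × 20 + 0.8 × 110 = 114. If none was, 10 + 20 + 88 = 118. So 117 is plausible as a count of children *receiving* peramivir. It cannot be a count *randomized* to it, as protocol 13.4 words it. The cohorts ever open to randomization hold 20 + 10 + 30 + 40 + 30 = 130, and 0.8 × 130 = 104 at most.
3. *Left out on the SAP's own scheme.* At most 10 + 20 = 30, and at least the 10 neonates.
4. *Left out under protocol version 6.0.* Let m be the number aged 28 days to <7 years who were randomized before amendment 3 (out of 20 + 10 + 30 = 60; not stated).
   - Left out = 10 + (60 − m) = 70 − m.
   - On peramivir = 10 + (60 − m) + 0.8m + 0.8 × 70 = 126 − 0.2m.

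| m | Left out | On peramivir | Share of peramivir left out |
|---|---|---|---|
| 60 | 10 | 114 | 9% |
| 45 | 25 | 117 | 21% |
| 40 | 30 | 118 | 25% |
| 20 | 50 | 122 | 41% |

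The synopsis says the cohort aged 2 to 7 was partly enrolled under randomization, so m is above 0 and fewer than 70 of 140 are left out. A peramivir total of exactly 117 needs m = (126 − 117)/0.2 = 45, which leaves out 25.

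**Related mismatches**
- SAP 6 lists age groups from 28 days, while protocol 13 has a 0-28 days group. Neonates lose their row in by-age displays, although this alone does not remove them from overall tables.
- SAP 5 promises listings for everyone enrolled, SAP 9 only for those randomized.
- SAP 2.1 starts the five-symptom diary group at 28 days, protocol 10.3.2 at birth.

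**The case against.** The best defence is that *randomized* here simply means allocated. SAP 4.3.8 defines the age of the neonatal cohort at the time of randomization. Protocol 12 limits PK sampling to subjects randomized to peramivir and then gives a rule for very small infants. Protocol 13.4 uses the word for a number that can only mean assigned. Because SAP 7 anticipates no other change, 5.3 may have been meant to reproduce the protocol's set. This makes inclusion the probable intent. It does not settle the text: SAP 4.2 sets being randomized against simply receiving peramivir, and SAP 5 and 5.2 say *enrolled* next to *randomized* in 5.1 and 5.3. A programmer has good reason to treat the terms as different.

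Second, part of the gap looks like version lag. The SAP's revision entry is dated 29 June 2016, and it still randomizes ages 2 to <18 years, which protocol version 6.0 does not. That is fair, and the bound of 70 depends on the newer protocol. But the SAP conflicts with its own design for neonates and for under-2s assigned directly.

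Third, the PK effect is limited. Table 14.4.1.1 is one descriptive table. The exposure-response population is drawn from ITTI, and the population PK modelling is a separate analysis. That stands.

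Fourth, listings might serve as a backstop. They are not a sure one, since SAP 9 restricts them to randomized subjects and SAP 10 labels the adverse event and laboratory listings ITT.

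**Conclusion.** The concern holds. As written, SAP 5.3 excludes every treated child who was assigned rather than randomized from the primary set for the primary objective. This contradicts protocol 13.5 and is not declared in SAP 7. The ITT definition has the same fault in both documents.

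The documents do not give the actual number. With full cohorts it is 10 to 30 on the SAP's scheme, and at least 10 but fewer than 70 of 140 under protocol version 6.0. If the peramivir total is exactly 117, it is 25 of 117 (21%). The whole neonatal cohort is lost in every case. No hypothesis is tested, so no error rate or power is affected. What is lost is the safety description of the youngest children. That inclusion was probably intended is a reason to correct the wording before the final analysis. The age-group omission belongs with this correction; the diary, listing and sample-size wording points are minor.

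**What to change.** - **SAP 5.3:** define Safety as *all subjects who receive any amount of study drug*. Removing the randomization condition is the essential step. I would also state that subjects are analysed by treatment received.
- **SAP 5.1 and protocol 13.5:** define ITT as *all subjects randomized or assigned to treatment*.
- **SAP 6:** define treatment group by treatment assignment, without *randomized*, and add the age group from birth to <28 days.
- **SAP 2.1 and 4.2:** bring the description of allocation into line with protocol version 6.0, and start the five-symptom diary group at birth as in protocol 10.3.2.
- **SAP 9:** prepare listings for all enrolled subjects, to agree with SAP 5, and relabel the listings in SAP 10 to match.
- **Protocol 13.4:** describe the figure of about 117 as subjects receiving peramivir, updated to the actual allocation.

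The cost is wording in the SAP and in protocol 13.4 and 13.5. No new data or patients are needed.

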#### 5.4. EXPOSURE-RESPONSE POPULATION

The exposure-response population will include all subjects in the ITTI population who have a quantifiable peramivir concentration on day 1 and have at least one post-baseline effectiveness assessment. This population will be used for all exposure-response analyses.

# 5.5. VIROLOGY POPULATION

The virology population will include all subjects in the ITTI population who have a laboratory-confirmed influenza infection denoted by a positive RT-PCR assay. This population will be used for all virologic analyses.

#### 6. STATISTICAL METHODS

Descriptive statistical methods will be used to summarize the data from this study. Data will be summarized by treatment group, age group, and study day/time, if appropriate. Unless stated otherwise, the term "descriptive statistics" refers to number of subjects (n), mean, median, standard deviation (SD), minimum, and maximum for continuous data and frequencies and percentages for categorical data. The term "treatment group" refers to randomized treatment assignment: single dose peramivir IV or oseltamivir BID for 5 days. The term "age group" refers to the following: 28 days - < 2 years,  $\ge$  2 years - < 7 years,  $\ge$  7 years - < 13 years, and  $\ge$  13 years - < 18 years. All data collected during the study will be included in data listings. Unless otherwise noted, the data will be sorted first by treatment group, age group, subject number, and then by date within each subject number.

The statistical analyses will be conducted with the SAS® software package version 9.2 or higher. All analyses will be subject to formal verification procedures. Specifically, results will be verified utilizing independent programming prior to issuance of the draft statistical report. All documents will be verified by the lead statistician to ensure accuracy and consistency of analyses.

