13. STATISTICS

Descriptive statistical methods will be used to summarize the data from this study. Data will be summarized by treatment group, age group, and study day/time, if appropriate. Unless stated otherwise, the term "descriptive statistics" refers to number of subjects (n), mean, median, standard deviation (SD), minimum, and maximum for continuous data and frequencies and percentages for categorical data. The term "treatment group" refers to treatment assignment: single dose peramivir IV or oseltamivir BID for 5 days. The term "age group" refers to the following: 0-28 days; 28 days -<2 years, ≥ 2 years -<7 years, ≥ 7 years -<13 years, and ≥ 13 years -<18 years. All data collected during the study will be included in data listings. Unless otherwise noted, the data will be sorted first by treatment group, age group, subject number, and then by date within each subject number.

The statistical analyses will be conducted with the SAS® software package version 9.2 or higher. All analyses will be subject to formal verification procedures. Specifically, results will be verified utilizing independent programming prior to issuance of the draft statistical report. All documents will be verified by the lead statistician to ensure accuracy and consistency of analyses.

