#### 6.3. SAFETY

#### **6.3.1.** Adverse Events

Adverse events will be mapped to a Medical Dictionary for Regulatory Activities (MedDRA) version 18.0 preferred term and system organ classification. If a subject experiences multiple events that map to a single preferred term, the greatest severity grade and strongest investigator assessment of relation to study medication will be assigned to the preferred term for the appropriate summaries. Should an event have a missing severity or relationship, it will be classified as having the highest severity and/or strongest relationship to study medication. Summaries of treatment-emergent AEs will include any AEs reported beginning with the initiation of study drug on Day 1. The occurrence of treatment-emergent adverse events (TEAEs) will be summarized by treatment group using preferred terms, system organ classifications, and severity. Separate summaries of treatment-emergent serious adverse events, treatment-emergent adverse events related to study drug, and events leading to the discontinuation of study will be generated. All adverse events reported will be listed for individual subjects showing both verbatim and preferred terms. All adverse events that occurred prior to the initiation of study treatment or more than 14 days post-study drug discontinuation will be excluded from the tables but will be included in the listings.

Missing onset dates will be imputed as previously outlined in Section 4.3.5 as required to determine treatment-emergent events.

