#### **6.3.3.** Clinical Laboratory Assessments

Descriptive summaries of the following selected (quantitative) clinical laboratory results will be presented by study visit and treatment group for each age group and overall: ALT, AST, Serum Creatinine, BUN, HGB, Albumin, and Alkaline Phosphatase. Laboratory abnormalities (toxicities) will be graded according to the DAIDS Table for Grading Adverse Events for Adults and Pediatrics (Publish Date: December 2004). The number and percentage of subjects experiencing treatment-emergent graded toxicities will be summarized by treatment group for each age group and overall. Laboratory toxicity shifts from baseline to Day 7 will be summarized by treatment group for each age group and overall.

All laboratory toxicities that occurred before the initiation of study treatment or more than 14 days post study drug discontinuation will be excluded from the tables but will be included in the listings.

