# **6.3.4.** Other Safety Analyses

Descriptive summaries of vital signs will be presented by study visit and treatment group for each age group and overall.

All abnormal physical examination findings will be summarized by study visit and treatment group for each age group and overall.

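### The SAP groups its safety tables by randomized assignment, not by drug received, and read literally leaves out children assigned peramivir without randomization

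*SAP*

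**What the plan says.** SAP section 6 sets the general rule for summaries: "Data will be summarized by treatment group, age group, and study day/time, if appropriate". It then says that treatment group "refers to randomized treatment assignment: single dose peramivir IV or oseltamivir BID for 5 days". The safety sections rely on that term without redefining it:

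- SAP 6.3.1: treatment-emergent adverse events "will be summarized by treatment group using preferred terms, system organ classifications, and severity".
- SAP 6.3.3: the number and percentage of subjects "experiencing treatment-emergent graded toxicities will be summarized by treatment group for each age group and overall".
- SAP 6.3.4: "Descriptive summaries of vital signs will be presented by study visit and treatment group for each age group and overall". Abnormal physical examination findings are handled the same way.

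SAP 5.3 defines the Safety population as "all randomized subjects who receive at least one partial dose/injection of study drug". That settles who is in the tables. It does not settle the arm in which a child is counted.

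The protocol is slightly different. Its section 13 says that treatment group "refers to treatment assignment: single dose peramivir IV or oseltamivir BID for 5 days", without the word 'randomized'. Its section 13.5 puts every subject who received a dose in the safety population. It has no rule on drug received either.

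**The concern.** The primary objective is the safety of peramivir compared with oseltamivir, and the primary endpoints are safety endpoints. A safety table is meant to show what happened to children exposed to a drug. Under the SAP's definition, a child assigned one drug and given the other has any adverse event or laboratory change reported under a drug that the child did not take. The oseltamivir arm is small, so one child is visible in its rates.

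The same wording has a second effect that does not depend on a dosing error. Some children are given peramivir by cohort rule and are never randomized. Read literally, they have no randomized assignment, so they have no treatment group under SAP section 6 and no place in the Safety population under SAP 5.3.

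**Working it through.** **1. Arm sizes.** The only arm size stated is in protocol 13.4: approximately 117 of up to 140 on peramivir. By subtraction, 140 − 117 = 23 on oseltamivir.

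The cohort caps and the 4:1 ratio in SAP 2.1 recover a similar figure:

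- 28 days to <2 years all randomized: 10 + 0.8 × 20 + 0.8 × 110 = 114 peramivir, 26 oseltamivir.
- 28 days to <2 years all on peramivir: 10 + 20 + 0.8 × 110 = 118 peramivir, 22 oseltamivir.

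The stated 117 lies between these. Under the current protocol, with x children aged 28 days to <7 years randomized before amendment 3 (at most 20 + 10 + 30 = 60), oseltamivir n = 0.2 × 70 + 0.2x = 14 + 0.2x. The figure 23 corresponds to x = 45. The limits of 14 (x = 0) and 26 (x = 60) both conflict with the protocol synopsis. It says that the 2 to 7 year cohort was partly enrolled under the earlier randomization and that the remaining children go to peramivir. I therefore use 23.

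**2. Effect of one mismatched child on an oseltamivir rate.** Take one child assigned oseltamivir and given peramivir, who has the event, with k other oseltamivir children having it. The rate is (k + 1)/n by assignment and k/(n − 1) by drug received.

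| Table | n | k | By assignment | By drug received | Difference |
|---|---|---|---|---|---|
| Overall | 23 | 0 | 1/23 = 4.3% | 0/22 = 0% | 4.3 points |
| Overall | 23 | 1 | 2/23 = 8.7% | 1/22 = 4.5% | 4.2 points (before rounding, 4.15) |
| 7 to <13 years | 0.2 × 40 = 8 | 0 | 1/8 = 12.5% | 0/7 = 0% | 12.5 points |
| 13 to <18 years | 0.2 × 30 = 6 | 0 | 1/6 = 16.7% | 0/5 = 0% | 16.7 points |

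If the mismatched child does not have the event, only the denominator changes. With k = 1, the rate is 1/23 = 4.3% by assignment and 1/22 = 4.5% by drug received, a difference of 0.2 points.

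**3. Effect on a peramivir rate.** The same child moves into the peramivir arm. With three other events, 3/117 = 2.6% becomes 4/118 = 3.4%, a change of 0.8 points. The change cannot exceed 1/118 = 0.85 points.

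**4. Children without randomization.**

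- SAP 2.1 and 4.2 say that children from birth to <28 days (up to 10) receive peramivir, and that children of 28 days to <2 years under protocol version 4.0 or later do too.
- Protocol 9.3 extends this to all children under 7 years after approval of amendment 3.
- SAP 5.3 and 6 nevertheless speak only of randomized subjects and randomized assignment.
- Protocol 13 and 13.5 do not use that restriction for treatment group or the safety population, so the SAP is narrower than the protocol here.
- SAP section 7 lists one change to the planned analyses, the count of antipyretic doses. The narrowing is therefore probably unintended.

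**The case against.** The strongest reply is that the mismatch is hypothetical and the trial's procedures make it unlikely.

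- Staff or other qualified personnel give the infusion and the first oseltamivir dose on site, and dosing is recorded (protocol 9.5). An infusion is hard to confuse with a capsule or suspension.
- A reader might infer that a failed IV line or a refusal would lead to the other drug. The documents provide no such path. Protocol 9.8.2 does not permit other influenza antivirals during study drug administration or follow-up, and a child who is never dosed leaves the Safety population. A mismatch would need a protocol deviation.
- After amendment 3 nobody is randomized to oseltamivir.
- SAP Table 14.1.2.1 and Listings 16.2.2, 16.2.4.2 and 16.2.5.1 would let a reader trace a misdosed child.
- No hypothesis is tested (protocol 13.3), so no error rate or decision rule changes.

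Most of this stands, and it limits the weight of the point. It does not remove it. Listings do not correct the primary tables. All oseltamivir children were allocated before amendment 3, so the period at risk contains the whole comparator arm. These arguments also do not touch the literal omission of non-randomized children.

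A reader might also infer that every analysis is affected. The documents do not support that. Assignment is the right basis for ITT and usual for ITTI. The exposure-response population is selected by measured peramivir concentration (SAP 5.4), and the concomitant medication summary names no arm split (SAP 6.3.2).

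**Conclusion.** The point holds for the safety tables and is a should-fix. The SAP states a grouping rule for its primary safety comparison that would place a misdosed child under the wrong drug, and neither document overrides it. "The safety population will be the primary population for all analyses" of safety data, so the membership wording in SAP 5.3 matters as well.

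The size is conditional. It assumes about 23 oseltamivir children, one mismatched child who has the event, and few other oseltamivir events. On those terms an oseltamivir rate moves by about 4 points overall, and by up to 12.5 or 16.7 points in the two older age groups. A peramivir rate moves by under 1 point. If there was no mismatch, this part of the rule distorts nothing.

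A reader might infer that the primary safety results are already distorted. The documents report no child who received the other drug and give no rate from which to estimate one, so they do not support that conclusion. The omission of non-randomized children rests on the literal text alone, and the sponsor probably does not intend it.

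**What to change.** - **SAP 5.3:** define the Safety population as all enrolled subjects who receive at least a partial dose of study drug, so that children given peramivir without randomization are included.
- **SAP 6 and 6.3:** add: *For the Safety population, treatment group is the study drug actually received; for ITT and ITTI it is the randomized or assigned treatment.* SAP 5.1 also restricts ITT to randomized subjects and should be reconciled in the same edit.
- **Listing 16.2.5.1:** flag any child whose assigned and received drugs differ.

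The cost is a few words of SAP text and one derived variable, using dosing data already recorded. No new data are needed, and nothing changes for randomized children if no mismatch occurred. The change should be made before database lock.
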